9.1 Disposition of Subjects

Summary tables by Treatment Sequence, Treatment Period, and total population will present for all subjects screened:

- The number of subjects screened.
- The number of screen failures incl. reasons for screen failure.
- The number of subjects per analysis set.
- The number and percentage of subjects completed each treatment period.
- The number and percentage of subjects treated in each treatment period.
- The number and percentage of subjects who completed each treatment period and the study.
- The number and percentage of subjects who prematurely discontinued by treatment period.

Percentages will be based on the number of subjects randomized.

Reasons for discontinuing the IP and withdrawing a subject from the study will be listed by subject.

Reasons for screened failures will be listed by subject.

9.2 Protocol Deviations

A summary of all key protocol deviations, including inclusion and exclusion deviations, will be provided by Treatment Sequence.

A listing of all protocol deviations will be provided.

Protocol deviations will be identified and classified into key/ non-key by CSLB. The final decision will be made in the DRM.

9.3 Demographic and Baseline Characteristics

The following summaries will be provided by Treatment Sequence and total:

- Demographic characteristics: sex (female, male, unknown), age (years provided by IRT), race (American Indian or Alaska Native, Asian, Black or African American, Native Hawaiian or Other Pacific Islander, White, Other), ethnicity (Hispanic or Latino, Not Hispanic or Latino, Not reported, Unknown), baseline height (cm), baseline body weight (kg), baseline BMI (kg/m²);
- In addition to summarization as a continuous variable, age will also be categorized and summarized (18-64 years, > 64 years).
- Demographic characteristics for the PP-IgPro10 and PP-IgPro20 analysis sets.
- Disease characteristics.
 - time since Systemic Sclerosis Initial diagnosis until randomization (months)
 - time since first Raynaud's phenomenon until randomization (months)
 - time since first non-Raynaud's phenomenon clinical manifestation until randomization (months)
 - ABO Blood Group and Rh Factor
 - Antiglobulin Test, Direct at Screening
 - Number of background therapy/immunosuppressants at Baseline (definition see [Section 9.4](#))

- Auto-antibodies at Baseline, categorized as follows:
 - Antinuclear Antibodies:
 - Negative (< 1:40), Positive (>= 1:40)
 - Centromere IgG Antibody (AU/mL):
 - Negative (<= 29), Equivocal/Positive (>= 30)
 - Fibrillarin (U3 RNP) Antibody:
 - Negative, Positive (all categories of positive combined)
 - PM/Scl-100 IgG Antibody:
 - Negative, Positive (all categories of positive and borderline combined)
 - RNA Polymerase III IgG Antibody (U):
 - Negative (<= 19), Positive (>= 20)
 - Ribonucleoprotein-70 IgG Antibody (AU/mL):
 - Negative (<= 29), Equivocal/Positive (>= 30)
 - Scl-70 IgG Antibody (AU/mL):
 - Negative (<= 29), Equivocal/Positive (>= 30)
- Past medical conditions present at screening.
- Current medical conditions present at screening.
- Smoking history

The following listings will be provided:

- Demographic characteristics.
- Disease characteristics.
- Past and current medical conditions.

9.4 Concomitant Medications

Prior and concomitant medications will be coded using WHO Drug Dictionary Enhanced (WHO-DDE) 2018 Mar B3 or more recent version, summarized and listed. The summary of concomitant medications will show the number and percentage (in proportion to subjects in Safety Analysis Set) of subjects taking prior and concomitant medications.

In the summary of concomitant medications, each subject is counted once within each unique term. For example, if a subject takes Amoxicillin on two separate occasions, the subject is counted only once under the ingredient “amoxicillin”.

Concomitant medication start and end dates are used select data to include in summaries as follows:

- Summary of Prior Medications: This summary will contain medications with end dates relative to treatment assigned to 'BEFORE'.
- Summary of Concomitant Medications: This summary will contain medications with start dates relative to treatment assigned to ('BEFORE', 'DURING PERIOD 1', 'DURING PERIOD 2') and end dates relative to treatment assigned to ('DURING PERIOD 1', 'DURING PERIOD 2', 'AFTER').
- Summary of Concomitant Medications with onset in IgPro10 Treatment Period: This summary will contain medications with start dates relative to treatment assigned to
 - Treatment Sequence A: 'DURING PERIOD 2',
 - Treatment Sequence B: 'DURING PERIOD 1'.
- Summary of Concomitant Medications with onset in IgPro20 Treatment Period: This summary will contain medications with start dates relative to treatment assigned to
 - Treatment Sequence A: 'DURING PERIOD 1',
 - Treatment Sequence B: 'DURING PERIOD 2'.
- Summaries of background therapy and immunosupprants intake at baseline: This summary will contain medications with
 - start dates relative to treatment assigned to 'BEFORE' AND
 - end dates relative to treatment assigned to ('DURING PERIOD 1', 'DURING PERIOD 2', 'AFTER') AND
 - indication for the medication is 'Study Indication (Systemic Sclerosis)' AND
 - ATC 2 code is L01 (ANTINEOPLASTIC AGENTS), L04 (IMMUNOSUPPRESSANTS) or H02 (CORTICOSTEROIDS FOR SYSTEMIC USE).
- Summary for concomitant medications used to treat COVID-19 associated adverse events

10 Efficacy

All efficacy analyses will be based on the ITT analysis set.

Summaries will be presented for the following combinations of Treatment Sequence and Treatment Period (respective Treatment Sequences [A/B] and Treatment Periods [1/2] are given in parentheses):

By Sequence

- Treatment Sequence A (A/1 and A/2)
- Treatment Sequence B (B/1 and B/2)
- Total

By Treatment

- IgPro20 (A/1 and B/2)
- IgPro10 (A/2 and B/1)

By Period – IgPro10

- Period 1 (B1)
- Period 2 (A2)

By Period – IgPro20

- Period 1 (A1)
- Period 2 (B2)

10.1 CCI

CCI

Table 6: CCI [Redacted]

CCI	[Redacted]	[Redacted]	[Redacted]	[Redacted]
[Redacted]	[Redacted]	[Redacted]	[Redacted]	[Redacted]
[Redacted]	[Redacted]	[Redacted]	[Redacted]	[Redacted]
[Redacted]	[Redacted]	[Redacted]	[Redacted]	[Redacted]
[Redacted]	[Redacted]	[Redacted]	[Redacted]	[Redacted]
[Redacted]	[Redacted]	[Redacted]	[Redacted]	[Redacted]

CCI	

10.2 Treatment Compliance

Treatment compliance for IgPro20 and IgPro10 will be measured as a percentage overall and summarized using descriptive statistics. A percentage between 80% and 120% is regarded as compliant to treatment.

Compliance (%) =

$100 * \text{total administered volume (mL) per subject} / \text{total planned volume (mL) per subject}$

11 Safety Analyses

All safety analyses will be based on the SAF analysis set.

11.1 Extent of Exposure

Exposure to the investigational product will be descriptively summarized by treatment.

For both **IgPro20** Treatment Periods and IgPro20 combined:

- Number of Weekly Infusions
- Planned and administered volume by Weekly Infusion and subject
- Administered total dose by subject
- Maximum infusion rate per infusion site by Infusion and subject
- Maximum volume per infusion site by Infusion and subject
- Duration of infusion by Infusion and Weekly Infusion
- Number of infusion sites per Infusion
- Duration of treatment

There are several levels of aggregation for study drug exposure.

Level 1: Infusion. Observation in database extract.

Level 2: Weekly Infusion. One Weekly Infusion consists of 2 Infusion.

Level 3: Subject. All Weekly Infusions of the IgPro20 Treatment Period for a subject.

Table 7: Derivation of Exposure Variables IgPro20

Variable	Infusion	Weekly Infusion	Subject
Total planned volume (mL)	n/a	derived	sum
Total administered volume (mL)	entered	sum	sum
Total number of infusion sites	entered	n/a	n/a
Maximal number of infusion sites used in parallel	entered	n/a	n/a
Actual total dose (g)	n/a	derived	derived
Maximum infusion rate per infusion site (mL/h)	entered	max	max
Maximum volume per infusion site (mL)	derived	max	max
Duration of Infusion	derived	sum	n/a
Duration of Treatment	n/a	n/a	derived

derived= see derivation rule below

sum= sum of values of the lower level of the same variable

max= maximum of the values of the lower level of the same variable

Total Planned Volume (mL)

Level: Weekly Infusion

The total planned volume is entered twice per week, once for each infusion. The value of the total planned volume will be taken from the entry of the first infusion of each week.

Actual Total Dose (g)

Level: Subject

$$\text{Actual Total Dose (g)} = \text{Total Administered Volume (mL)} * 0.2 \text{ g/mL}$$

Level: Weekly Infusion

$$\text{Actual Dose (g)} = \text{Administered Volume in respective week (mL)} * 0.2 \text{ g/mL}$$

Maximum volume per infusion site (mL)

Level: Infusion

Maximum volume per infusion site (mL) =
Total administered volume (mL) / maximal number of infusion sites used in parallel

Duration of Infusion

Level: Infusion

duration (min) = end time (min) – start time (min)
if duration < 0 (i.e., end is on the next day) then duration = duration + 24 * 60

Duration of treatment

Level: Subject

duration (days) =
last day with IgPro20 treatment – first day of IgPro20 treatment + 1

For both **IgPro10** Treatment Periods and IgPro10 combined:

- Number of Infusion Cycles
- Planned and administered volume by Infusion Cycle and subject
- Administered total dose by Infusion Cycle and subject
- Duration of infusion by Infusion and Infusion Cycle
- Duration of treatment
- Maximum infusion rate by subject (mL/h, mL/kg/h, mg/kg/min)

There are several levels of aggregation for study drug exposure.

Level 1: Infusion. Observation in database extract.

Level 2: Infusion Cycle. One Infusion Cycle consists of 2-5 Infusions.

Level 3: Subject. All Infusion Cycles of the IgPro10 Treatment Period for a subject.

Table 8: Derivation of Exposure Variables IgPro10

Variable	Infusion	Infusion Cycle	Subject
Total planned volume (mL)	n/a	derived	sum
Total administered volume (mL)	entered	sum	sum
Initial infusion rate (mL/h)	entered	n/a	n/a
Initial infusion rate (mL/kg/h, mg/kg/min)	derived	n/a	n/a
Maximum infusion rate (mL/h, mL/kg/h, mg/kg/min)	derived	max	max
Actual total dose (g)	n/a	derived	derived
Duration of infusion	derived	sum	n/a
Duration of treatment	n/a	n/a	derived

derived= see derivation rule below

sum= sum of values of the lower level of the same variable

max= maximum of the values of the lower level of the same variable

Total Planned Volume (mL)

Level: Infusion Cycle

The total planned volume is entered once for each infusion. The value of the total planned volume will be taken from the entry of the first infusion of each Infusion Cycle.

Initial Infusion Rate (mL/kg/h)

Level: Infusion

$$\text{Initial Infusion Rate (mL/kg/h)} = \text{Initial Infusion Rate (mL/h)} / \text{reference weight (kg)}$$

Reference body weight is the baseline body weight. After a change of planned volume for the week, the most recent body weight before the change of planned volume is the reference weight.

Initial Infusion Rate (mg/kg/min)

Level: Infusion

$$\text{Initial Infusion Rate (mg/kg/min)} = 100 \text{ mg/mL} * \text{Initial Infusion Rate (mL/h)} / \text{reference body weight (kg)} / 60$$

Maximum Infusion Rate (all units)

Level: Infusion

The maximum infusion rate is the maximum of the initial infusion rate and all infusion rates after a change of infusion rate.

Actual Total Dose (g)

Level: Infusion Cycle, Subject

$$\text{Actual Total Dose (g)} = \text{Total Administered Volume (mL)} * 0.1 \text{ g/mL}$$

Duration of Infusion

Level: Infusion

$$\text{duration (min)} = \text{end time (min)} - \text{start time (min)}$$

if duration < 0 (i.e., end is on the next day) then duration = duration + 24 * 60

Duration of treatment

Level: Subject

$$\text{duration (days)} = \text{last day with IgPro10 treatment} - \text{first day of IgPro10 treatment} + 1$$

The listing of individual subject data will include all variables presented in the summary tables.

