5.1.3 Dosing and Administration of Investigational Products

The investigator (or delegate) will administer or dispense IgPro20 or IgPro10 only to subjects included in this study following the procedures set out in this study protocol.

IgPro20 Administration

Subjects will receive SC IgPro20 infusions at 2 sessions at a total dose of 0.5 g/kg every week. The total dose / volume of IgPro20 will be calculated based on body weight. Body weight will be measured at every site visit before infusion and possible adjustment to dose / volume may occur as described in [Section 3.2](#). Subjects weighing ≥ 100 kg will receive a fixed dose of 50 g, every week. A dosing regimen of 2 times a week (eg, Day 1 and Day 3 or Day 4 each week) will be followed.

The SC infusions should be performed at appropriate infusion sites with sufficient normal skin areas or **CCI** ≤ 2 and any other skin conditions precluding SC infusion (eg, on the abdomen, thighs, and / or lateral hip). Infusion sites in the normal skin or **CCI** ≤ 2 in abdominal area are recommended in this study, with at least 2 inches (~5 cm) between infusion sites. Other anatomic locations approved for SC infusions should be used with extreme caution and only if recommended by the study investigator. The number of infusion sites depends on the total volume to be administered and tolerability, not to exceed 4 infusion sites simultaneously. Any changes in volume or rate of infusion should be discussed with the

Principal Investigator. The maximum rate and the maximum volume per infusion site should not be exceeded, and any increase rate or volume should be done gradually, as tolerated. The maximum rate and the maximum volume per infusion site is recommended:

Volume	1st 2 infusion sessions : ≤ 20 mL/site; all subsequent infusions: ≤ 50 mL/site as tolerated
Rate	1st 2 infusion sessions : ≤ 20 mL/h/site; all subsequent infusions: ≤ 50 mL/h/site as tolerated

Note: Attempts to reach the maximum values for both the volume and flow rate per infusion site during the same infusion should be performed gradually with caution and strictly as tolerated.

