Detailed information in reference to IgPro20 administration (eg, infusion start time / day, infusion stop time / day, number of infusion sites, infusion rate, total administered IgPro20 dose, site of administration, and whether infusion was omitted, interrupted or stopped and reason) will be documented on the IgPro20 infusion form completed by site personnel or home health nurse qualified to administer IgPro20. Refer to the Site IP Manual for further information.

IgPro10 Administration

Subjects will receive IV IgPro10 infusions split over 2, 3, 4 or 5 consecutive days, depending on total dose and individual tolerability, at a total dose of 2 g/kg every 4 weeks. The total dose / volume of all IPs will be calculated based on body weight. Body weight will be collected before each infusion and possible adjustment to dose / volume may occur as described in [Section 3.2](#). Subjects weighing ≥ 100 kg will receive a fixed dose of 200 g, every 4 weeks.

Recommended Rate of Infusion:

First infusion session	
Rate of 0.3 mL/kg/h (30 mg/kg/h; 0.005 mL/kg/min; 0.5 mg/kg/min);
 
If well tolerated within 30 min: increase to 0.6 mL/kg/h (60 mg/kg/h; 0.01 mL/kg/min; 1.0 mg/kg/min) for another 30 min;
 
If well tolerated within an additional 30 min: increase to 1.2 mL/kg/h (120 mg/kg/h; 0.02 mL/kg/min; 2.0 mg/kg/min).

Second infusion session	
Rate of 0.3 mL/kg/h (30 mg/kg/h; 0.5 mg/kg/min; 0.005 mL/kg/min);
 
If well tolerated within 30 min: increase to 0.6 mL/kg/h (60 mg/kg/h; 0.01 mL/kg/min; 1.0 mg/kg/min) for another 30 min;
 
If well tolerated within an additional 30 min can increase to 1.2 mL/kg/h;
 
If well tolerated within an additional 30 min can increase to 2.4 mL/kg/h.

Subsequent infusions	
Initial rate of 0.3 mL/kg/h (30 mg/kg/h; 0.005 mL/kg/min; 0.5 mg/kg/min), incremental increases of infusion rate can exceed 1.2 mL/kg/h as tolerated (up to the maximum recommended infusion rate of 4.8 mL/kg/h [480 mg/kg/h; 0.08 mL/kg/min; 8 mg/kg/min]).

Recommended Rate of Infusion in Subjects with Renal Dysfunction:

First infusion	
Rate of 0.3 mL/kg/h (30 mg/kg/h; 0.005 mL/kg/min; 0.5 mg/kg/min);
 
If well tolerated within 30 min: increase to 0.6 mL/kg/h (60 mg/kg/h; 0.01 mL/kg/min; 1.0 mg/kg/min);
 
If well tolerated within an additional 30 min: increase to 1.2 mL/kg/h (120 mg/kg/h; 0.02 mL/kg/min; 2.0 mg/kg/min).

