LLN	Lower limit of normal
CCI	CCI
MedDRA	Medical Dictionary for Regulatory Activities
CCI	CCI
PFT	Pulmonary function test
CCI	CCI
PID	Primary immunodeficiency
PK	Pharmacokinetics
SAE	Serious adverse event
SAF	Safety analysis set
SAP	Statistical analysis plan
SC	Subcutaneous
SD	Standard deviation
CCI	CCI
SMQ	Standardized MedDRA queries
SOC	System Organ Class
SSc	Systemic sclerosis
CCI	CCI
TEAE	Treatment-emergent adverse event
TEE	Thromboembolic event
CCI	CCI
ULN	Upper limit of normal
CCI	CCI

Glossary of Terms

Term	Definition
Baseline Value	The most recent assessment before the first infusion in Treatment Period 1.
End of Study (EOS)	The follow-up telephone call occurs 4 weeks after completing study treatment or early termination follow-up visit, whichever occurs later.
End of Treatment (EOT)	End of treatment is either end of Week 32 for completed subjects or at early termination visit.
Infusion	
IgPro10 An infusion comprises all IP exposure on one day of infusion. In the IgPro10 Treatment Periods, there are 2 to 5 consecutive days of infusions and so 2 to 5 Infusions planned per 4-week period.
 
IgPro20 An infusion comprises all IP exposure on one day (one session). In the IgPro20 Treatment Periods, there are 2 sessions and so 2 infusions planned per week.

Infusion Cycle (IgPro10 only)	One Infusion Cycle consists of 2, 3, 4 or 5 consecutive days of infusions with a planned total dose of 2 g/kg IgPro10 every 4 weeks. There are 4 planned Infusion Cycles of IgPro10 per IgPro10 Treatment Period in each Treatment Sequence.
Weekly Infusions (IgPro20 only)	A Weekly Infusion consists of 2 sessions (2 Infusions) with a planned total dose of 0.5 g/kg IgPro20 per week. There are 14 Weekly Infusions of IgPro20 per IgPro20 Treatment Period per each Treatment Sequence.
Infusion Session (IgPro20 only)	One Infusion Session consists of 1 infusion day. There are 2 Infusion Sessions within each weekly infusion with a planned total dose of 0.5 g/kg IgPro20 per week.
Protocol Deviation	
All instances when either subjects who have been entered in the study and / or the study sites deviate from the IEC / IRB-approved study protocol.
 
A key protocol deviation is any protocol deviation that could have a significant effect on the subject's safety, rights, or welfare and / or on the integrity of the study data.

Reference Visit	Reference visit for Treatment Period 1 is Week 1. Reference visit for Treatment Period 2 is Week 17.

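### SAP 11.1 divides whole-session IgPro20 volume by the sites used in parallel, so its maximum volume per site is not a true maximum and puts complying first-week sessions of more than 80 mL above the 20 mL/site limit

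*SAP*

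**What the plan says.** SAP 11.1 plans to summarise "Maximum volume per infusion site by Infusion and subject" for IgPro20. At the infusion level the variable is derived as "Total administered volume (mL) / maximal number of infusion sites used in parallel". Table 7 then takes the maximum over infusions for the Weekly Infusion and Subject levels. The SAP glossary sets the scope of the numerator for IgPro20: "An infusion comprises all IP exposure on one day (one session"). Table 7 also has a separate entered field, "Total number of infusion sites", which this derivation does not use. SAP 11.1 adds that the individual listing carries every summarised variable.

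Protocol 5.1.3 fixes the administration. The weekly 0.5 g/kg is given in two sessions through a number of sites "not to exceed 4 infusion sites simultaneously". The volume limits are "1st 2 infusion sessions : ≤ 20 mL/site; all subsequent infusions: ≤ 50 mL/site as tolerated". On their status it says "The maximum rate and the maximum volume per infusion site should not be exceeded", and the following sentence calls the values recommended. The items it gives as examples for the infusion form include "number of infusion sites, infusion rate, total administered IgPro20 dose, site of administration". The volume given at each site is not among them.

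**The concern.** The numerator and denominator cover different things. The volume is everything infused that day, including through sites opened after others were finished. The divisor counts only sites running at the same moment. Because Table 7 enters the two site counts separately, the SAP itself allows them to differ.

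Protocol 3.3.2 gives subcutaneous volume and skin safety as the reasons for not dosing IgPro20 above 0.5 g/kg/week in systemic sclerosis. Readers will therefore look to volume per site when judging tolerability. A summary and listing that show sessions above 20 mL/site, when every site stayed within the limit, would misdescribe how the product was given.

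**Working it through.** The documents give no figure for this variable, so there is nothing of the plan's own to reproduce. One input check: 0.5 g/kg x 100 kg = 50 g, which matches the fixed weekly dose from 100 kg in Protocol 5.1.3.

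**Inputs.** Concentration 0.2 g/mL (Protocol 5.1.1). From Protocol 5.1.3: 0.5 g/kg/week in 2 sessions, at most 4 sites at once, 20 mL/site in the first 2 sessions (the first IgPro20 week) and 50 mL/site afterwards. Body weights are not in the documents; 50 to 100 kg is assumed.

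**Threshold weight.** Weekly volume = 0.5 / 0.2 = 2.5 mL/kg, or 1.25 mL/kg per session if split equally. Four parallel sites at 20 mL carry 4 x 20 = 80 mL per session, or 160 mL over the first two sessions. 160 / 2.5 = 64 kg. Above 64 kg the weekly volume exceeds 160 mL, so however it is split at least one session exceeds 80 mL. A subject who takes the full dose and keeps the limit must then use a further site in succession.

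**SAP value against mean volume per site.** First-week session with an equal split, V = 1.25 x weight, the fewest sites that keep 20 mL/site, and 4 in parallel:

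| Weight (kg) | V (mL) | Sites | SAP value, V/4 | Mean, V/sites | Ratio |
|---|---|---|---|---|---|
| 60 | 75 | 4 | 18.8 | 18.8 | 1.00 |
| 64 | 80 | 4 | 20.0 | 20.0 | 1.00 |
| 65 | 81.25 | 5 | 20.3 | 16.3 | 1.25 |
| 70 | 87.5 | 5 | 21.9 | 17.5 | 1.25 |
| 80 | 100 | 5 | 25.0 | 20.0 | 1.25 |
| 90 | 112.5 | 6 | 28.1 | 18.8 | 1.50 |
| 100 | 125 | 7 | 31.3 | 17.9 | 1.75 |

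From 65 kg on, V/4 exceeds 20 mL. The true maximum is at most 20 mL because the limit was kept, so the overstatement does not depend on how the volume was spread over the sites. Fewer sites in parallel would widen the gap: with 2 in parallel, 80 kg gives 100/2 = 50.0 against a mean of 20.0.

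**Behaviour as a maximum.** Take 100 mL through 5 sites with 4 in parallel, so the SAP value is 25:
- 20, 20, 20, 20 and 20 mL: true maximum 20, mean 20. The SAP value is too high.
- 15, 15, 15, 15 and 40 mL (allowed after the first two sessions): true maximum 40, mean 20. The SAP value is too low.

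If all sites run in parallel, the two counts agree and the SAP value is simply the mean.

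**Reach.** After the first two sessions, 4 x 50 = 200 mL exceeds the largest equal-split session of 125 mL, so succession is no longer forced. It is forced in at most 2 of the 28 planned sessions. At subject level the maximum over infusions applies. An 80 kg subject who later takes 100 mL through 2 parallel sites has a value of 100/2 = 50.0, which replaces the first-week 25.0 and is correct if the two sites shared equally. A 100 kg subject who stays at or below 20 mL/site throughout, with 7 sites and 4 in parallel each time, would carry 31.3 where the mean is 17.9.

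**The case against.** A reader might infer that the formula overstates the maximum whenever sites are used in succession. The 15+15+15+15+40 mL example shows that it can understate it. The general statement holds only against the mean. Against the true maximum, overstatement is certain only in the first-week case above.

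A second objection is that dividing by the total site count does not repair the maximum. That stands: a mean never exceeds the maximum, and in the same example it gives 20 against a true 40, further away than the SAP's 25. The replacement is a different variable and must be labelled as one.

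Third, the definitions of the site counts on the case report form are not shown. Protocol 1.4.1.3 mentions leakage and poor needle placement. If the total includes sites that were re-needled without receiving volume, dividing by it would understate volume per site. This stands as something to confirm.

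Fourth, the reach is small. At most two sessions per subject are forced, the volume limit is also described as recommended, and escalation usually sets the subject-level value. All of this stands and bears on severity. It does not make the rule right for the sessions it affects.

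A reader might also infer that complying sessions would be recorded as protocol deviations, or that ISR results would be distorted. The documents support neither. SAP 9.2 leaves deviations to the sponsor and the data review meeting and does not mention this variable. The ISR rate in SAP 11.2 uses counts of reactions and infusions only.

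**Conclusion.** The derivation is wrong as written, and the point is minor. Applied literally, it gives an exposure variable that is not a maximum and that exceeds the mean volume per site whenever sites are used in succession. It shows more than 20 mL/site for every first-week session above 80 mL in which the limit was kept. Any subject above 64 kg given the full dose in two sessions has at least one first-week session above 80 mL.

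Under equal sessions, the fewest sites and 4 in parallel, the excess over the mean is 1.25-fold at 70 and 80 kg and 1.75-fold at 100 kg. At or below 64 kg there is no error under those assumptions. How many subjects are affected depends on weights and infusion practice that the documents do not give.

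The effect is confined to a descriptive exposure summary and its listing. ISR counts, ISR rates and PK results are unaffected; the PK dose normalisation in SAP 12.3 uses total volume, not volume per site.

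**What to change.** In SAP 11.1 and Table 7:

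- Infusion level: *Mean volume per infusion site (mL) = Total administered volume (mL) / Total number of infusion sites*.
- Weekly Infusion and Subject level: keep the maximum, labelled *maximum of the infusion-level mean volume per site*.
- Keep the number of sites used in parallel as a separate descriptor.
- State that a true maximum cannot be derived without the volume given at each site.
- Confirm from the case report form that the total site count excludes sites re-needled without receiving volume.

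The cost is one formula and the labels that go with it. Both counts are already entered for each infusion, so no new data are needed, and values change only where sites were used in succession. If the SAP can no longer be amended, the change can be reported in the clinical study report, as SAP section 7 provides for deviations from the planned analyses. There are two drawbacks. A mean hides uneven volumes between sites, and comparability is lost with any earlier report that used the parallel-site rule; whether one exists is not known.
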